5.3.1 Unscheduled Assessments

Both scheduled and unscheduled assessments, including early termination visits, will be considered for planned timepoint summaries. All assessments will be presented in data listings.

5.3.2 Multiple Measurements within Visit Windows

If more than one assessment falls within a given window then the assessment closest to the target study day will be selected for the by-visit summaries. If two assessments are equidistant from the target day then the chronologically last assessment will be used for summary. Exceptions may be made for incomplete assessments, in which case, more complete assessments may be given priority. Details are provided in a separate programming conventions document.

For safety summaries where the most extreme values should be selected, e.g. overall post-baseline minimum and overall post-baseline maximum, all non-missing post-Baseline values should be considered, regardless of whether the value is selected for the by-visit summaries. All results will be presented in data listings.

5.4 Data Handling Conventions

5.4.1 Missing or Incomplete Date for Last Dose of Study Drug

In the Safety Analysis Set, if the last dose date of study drug is missing for a subject who completed or early terminated from the study, then the date of the end-of-study/early termination visit will be used in the calculation of treatment duration. For the incomplete last dose date of the study drug, the imputation algorithms will be detailed in the analysis dataset specification document. The missing or incomplete dates will be displayed in the data listings as reported on the eCRF rather than the imputed dates.

For data summarizations before final database lock, if a subject is still ongoing, then this subject's last dose date will be imputed using the database extract date.

5.4.2 Missing or Incomplete Dates for Concomitant or Post-Treatment Medications

Missing or incomplete medication start or end dates will be imputed for the purpose of determining whether the medications are taken concomitantly (see Section 10 for definition). When the chronological order of medication use relative to the study drug treatment period is unclear due to missing or incomplete date(s), the medication will be considered as concomitant. The imputation algorithms will be detailed in the analysis dataset specification document. The missing or incomplete dates will be displayed in the data listings as reported on the eCRF rather than the imputed dates.

5.4.3 Missing or Incomplete Dates for Adverse Events

Missing or incomplete adverse event (AE) start dates will be imputed for the purpose of determining whether the AEs are treatment-emergent (see Section 14.1 for definition). When the chronological order of an AE onset relative to the study drug treatment period is unclear due to missing or incomplete date(s), the AE will be considered as treatment-emergent. The imputation algorithms will be detailed in the analysis dataset specification document. The missing or incomplete dates will be displayed in the data listings as reported on the eCRF rather than the imputed dates.

5.4.4 Missing Severity Assessment for Adverse Events

If the severity is missing for a treatment-emergent AE, a severity of "Severe" will be assigned. The imputed values for severity assessment will be used for incidence summaries, and the actual values will be presented in data listings.

5.4.5 Missing Relationship to Study Drug for Adverse Events

If the relationship to study drug is missing for a treatment-emergent AE, a causality of "Related" will be assigned. The imputed values for relationship to study drug will be used for incidence summaries, and the actual values will be presented in data listings.

5.4.6 Character Values of Clinical Laboratory Variables

If the reported value of a clinical laboratory variable cannot be used in a summary due to, for example, a character string reported for a numeric variable, an appropriately determined coded value will be used in the summary. The coding algorithms will be detailed in the analysis dataset specification document. The actual values as reported in the database will be presented in data listings.

6 SUBJECT DISPOSITION

The number of sites that screened at least 1 subject, number of sites that randomized at least 1 subject, number of subjects screened, and number of unique subjects screened will be summarized. In addition, the number of subjects enrolled at each site will also be tabulated. The number and percentage of subjects who completed the study or discontinued (all discontinued and by discontinuation reason) will also be summarized for the Randomized, Safety, and Full Analysis sets. A summary by region for the Safety Analysis set will also be presented.

For subjects who were not included in the first interim analysis (IA-1) (see Section 16.2), early terminations of subjects due to COVID-19 related reasons will be captured in the eCRFs and summarized.

For randomized subjects, the number and percentage of subjects in the analysis sets will be summarized. A listing will be provided displaying all subjects excluded from the analysis sets (if any), and will include reason(s) for exclusion.

For subjects who participate in the screening phase and are screen failures, their demographics information (including age, sex, and primary race), screen failure reasons (the specific inclusion/exclusion criterion [or criteria] not met or other reason) and protocol version will be listed. If a subject is re-screened, then the re-screening subject ID and the final enrollment status (whether eventually enrolled) will also be displayed in this listing. In addition, the frequency that the screen failure reasons are reported will also be summarized. Note that a subject may be deemed ineligible for multiple inclusion/exclusion criteria and may be allowed to rescreen with the permission of the Medical Monitor, provided the screen failure was due to a temporary condition that subsequently resolved.

For subjects who were not included in IA-1, screen failures due to COVID-19 will be captured in the eCRFs, and summarized.

7 PROTOCOL DEVIATIONS

Protocol deviations will be reviewed periodically over the course of the study. The review process, definition of the deviation categories, and the classification of a deviation as major

or minor will be detailed in the Protocol Deviation Management Plan. For subjects who were not included in IA-1, protocol deviations will also be assessed with respect to relationship to COVID-19.

For randomized subjects, a summary of the number and percentage of subjects with major protocol deviations for each deviation category will be presented in three ways: all protocol deviations, COVID-19 related protocol deviations, and non COVID-19 related protocol deviations.

Similarly, three data listings of major protocol deviations will be provided: All deviations, COVID-19 related protocol deviations, and non COVID-19 related protocol deviations. Additionally, a data listing of all minor COVID-19 related protocol deviations will be provided.

In order to assess the potential impact of COVID-19 on missed visits, the proportion of missed visits will be tabulated by treatment arm for the Safety analysis set, computed as the number of total number missed visits divided by the total number of expected visits. This will be tabulated separately for IA-1 subjects, and subjects enrolled after IA-1, as a proxy for pre- and post-COVID-19 analyses.

8 DEMOGRAPHICS AND OTHER BASELINE CHARACTERISTICS

Demographics and Baseline characteristics will be summarized for the Randomized, Safety, and Full Analysis sets using descriptive statistics. Summaries by region using the Safety Analysis set will also be presented.

8.1 Demographics

Demographic variables include age, sex, primary race (subjects of multi-racial background can only identify/select one primary race on eCRF, or choose "other" and specify), ethnicity, height, weight, body mass index (BMI), region, subject living situation, and partner/caregiver relationship.

The reported age reflects a subject's age at the informed consent date. Age and BMI will be presented as both continuous and categorical variables. Age categories will be presented as <65, 65 to 74, 75 to 84, and ≥85 years old. BMI categories (kg/m²) will be presented as <25, 25 to 30, and >30.

8.2 Disease Characteristics

Disease characteristics at Baseline will be summarized for the Randomized, Safety, and Full Analysis sets using descriptive statistics. MMSE total score, CGI-S, EQ-5D-5L VAS, SDI total score, and ESRS-A total score will be presented as continuous variables. CGI-S will be presented as a categorical variable using categories of 1 to 7, and MMSE total score will be

presented as a categorical variable using categories of ≤10, 11 to 17, 18 to 24, and 25 to 30. The number and percentage of subjects reporting suicidal ideation and suicidal behavior within the past 6 months and lifetime will be tabulated (for those subjects assessed with C-SSRS), and number and percentage of subjects reporting suicidality within the past 3 months and lifetime will be tabulated (for those subjects assessed with the GCAS).

Neuropsychiatric history will be summarized descriptively for continuous and categorical variables. Informed consent date will be used as the reference date when calculating duration of disease variables.

For both the Disease Characteristics and Neuropsychiatric History, summaries by region will be presented using the Safety Analysis Set.

8.3 Neuropsychiatric Inventory (NPI)

NPI will be summarized at Baseline for the Randomized, Safety and Full Analysis sets. Each of the individual domain total scores will be presented as continuous variables using descriptive statistics.

9 MEDICAL HISTORY

Medical and surgical history data will be coded using Medical Dictionary for Regulatory Activities (MedDRA) version 20.0 or newer. The subject incidence will be summarized for each system organ class (SOC) and preferred term for the Safety Analysis Set and Full Analysis Set. A subject will be counted only once per SOC or per preferred term for the summary.

A listing of the SOC, preferred term, body system, verbatim term for the medical history condition/event, start and stop dates (when available), and an indicator for whether or not the condition is ongoing at Screening will be provided.

10 PRIOR, CONCOMITANT, AND POST-TREATMENT MEDICATION

Medications will be coded using WHO Drug Dictionary (WHODRUG-DDE-B2) 2018 March or newer version. For concomitant medications, the number and percentage of subjects taking each drug class (ATC Level 3) and medication preferred term will be tabulated. A subject will be counted only once per drug class or per medication preferred term for the summary. Prior, concomitant, and post-treatment medications will be summarized separately using the Safety Analysis Set.

10.1 Prior Medication

Prior medication is defined as any medication with a start and stop date prior to the date of the first dose of study drug.

10.2 Concomitant Medication

Concomitant medication is defined as any medication with a start date prior to the date of the first dose of study drug and continuing after the first dose of study drug, or with a start date between the dates of the first and last doses of study drug, inclusive.

10.3 Post-Treatment Medication

Post-treatment medication is defined as any medication with a start date after the last dose of study drug.

10.4 COVID-19 Related Medications

For those subjects not included in IA-1, relationship to COVID-19 will be assessed by the investigator as detailed in the DMP Appendix B. Concomitant and post-treatment medication analyses described in Section 10.2 and Section 10.3 above will also be summarized by relationship to COVID-19 (Not related to COVID-19 vs. Related to COVID-19).

11 EXTENT OF EXPOSURE AND TREATMENT COMPLIANCE

Summaries of exposure and compliance to study drug will be provided for the Safety Analysis Set and Full Analysis Set.

11.1 Exposure to Study drug

Pimavanserin dose levels are expressed as free base.

Duration of exposure is calculated as follows:

Duration of exposure = last study drug dose date – first study drug dose date + 1

For the categorical presentation of duration of exposure the number and percentage of subjects in each of the following categories will be displayed: <1 week (1 to 6 days), 1 to <2 weeks (7 to 13 days), 2 to <4 weeks (14 to 27 days), 4 to <6 weeks (28 to 41 days), 6 to <8 weeks (42 to 55 days) and ≥8 weeks (≥56 days).

Kaplan-Meier curves of duration of exposure will also be provided for each treatment group.

11.2 Measurement of Study Drug Compliance

Study drug compliance (in percentage) for a given subject is calculated as follows:

Study drug compliance will be summarized descriptively as both continuous and categorical variables. For the categorical presentation, the number and percentage of subjects in each of the following categories will be presented: <80%, 80 to 120%, and >120%.

12 EFFICACY ANALYSES

All efficacy analyses will be performed using the Full Analysis Set and the planned treatment assignments based on the randomization schedule. Descriptive summaries of all efficacy endpoints will be provided.

12.1 Exploratory Efficacy Endpoints

All of the efficacy endpoints are considered exploratory, and include the following:

- Change from Baseline to Week 8 in CGI-S score for neuropsychiatric symptoms
- CGI-I score at Week 8 for neuropsychiatric symptoms
- Change from Baseline to Week 8 in SDI score
- Change from Baseline to Week 8 in EQ-5D-5L scores (VAS and 5 level descriptive system)

12.2 Adjustment for Covariates

For continuous variables (except CGI-I) analyzed using a mixed model for repeated measured (MMRM) or an analysis of covariance (ANCOVA), the Baseline value of the endpoint being analyzed and region will be included as covariates as described in Sections 13.2 and 13.3. For CGI-I the Baseline CGI-S score and region will be included as covariates in the MMRM and ANCOVA analyses, and for CGI-I responder analyses region will be included as a stratification factor.

12.3 Handling of Missing Data

For selected endpoints missing values will be imputed with the previous observed value (including Baseline) for that subject, i.e. last observation carried forward (LOCF).

12.4 Multiple Comparisons/Multiplicity

No adjustments will be made for multiple comparisons for comparisons across multiple endpoints and across multiple subgroups.

12.5 Examination of Subgroups

Treatment comparisons will be made with respect to exploratory efficacy and secondary safety variables separately for each subgroup by:

• Dementia related psychosis (DRP) (yes):

- Subjects with dementia from any cause, and having either a Baseline NPI delusions or hallucinations score (frequency × severity) ≥ 2
- Primary cause of dementia due to Alzheimer's disease (AD) (yes):
 - Subjects with primary cause of dementia due to AD
- Alzheimer's disease psychosis (ADP) (yes)
 - Subjects with AD as the primary cause of dementia, and having either a Baseline NPI delusions or hallucinations score (frequency × severity) ≥ 2
- Other-dementia psychosis (yes)
 - Subjects with vascular dementia, frontotemporal dementia-spectrum disorders, or dementia with Lewy bodies, and having either a Baseline NPI delusions or hallucinations score (frequency × severity) ≥ 2

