1.3.1 Parkinson's Disease Psychosis Program

The scope of the development program for pimavanserin is the largest ever conducted in PDP. At the time of approval, 616 mostly older, late-stage PDP subjects had been evaluated in 16 countries over a span of >10 years. Clinically meaningful efficacy was established in Study ACP-103-020, a 6-week, placebo-controlled Phase 3 study (Cummings et al. 2014). This efficacy was supported by data from additional short-term Phase 2b/3 studies. In Study ACP-103-020, pimavanserin 34 mg consistently demonstrated statistically significant efficacy across multiple and independent endpoints, subject subgroups, and sensitivity analyses. Improvements in sleep and daytime wakefulness were also observed. These clinical benefits were achieved without worsening of Parkinson's disease motor symptoms and without a number of other safety concerns associated with atypical antipsychotics.

Pimavanserin is considered to be generally safe and well tolerated. Across all clinical studies of pimavanserin, the most frequently reported treatment-emergent adverse events (TEAEs) were in the central nervous system (CNS), gastrointestinal, and psychiatric systems. Most events were mild to moderate in intensity. The most common CNS TEAEs included dizziness (including postural), headache, and somnolence (drowsiness). Common gastrointestinal disturbances included dyspepsia, nausea, constipation, and vomiting. Severe nausea and vomiting were dose limiting in a few cases. Reported psychiatric conditions included agitation, insomnia, and confusional state.

Clinical and nonclinical safety pharmacology studies of pimavanserin suggest a potential risk for QT prolongation. The magnitude of effect in humans has been assessed in a thorough QT study with doses of pimavanserin ranging from 17 to 68 mg. In the Phase 3 PDP program, an average prolongation of approximately 5 to 8 ms was observed with pimavanserin 34 mg.

The US package insert for pimavanserin has a boxed warning that elderly patients with dementia-related psychosis treated with antipsychotic drugs are at an increased risk of death. Pimavanserin is not approved in the treatment of patients with dementia-related psychosis unrelated to the hallucinations and delusions associated with Parkinson's disease psychosis.

Additional information is provided in the pimavanserin Investigator's brochure and in the NUPLAZID® (pimavanserin) US package insert.

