4.2 Inclusion Criteria

A subject must meet all of the following inclusion criteria to be eligible for participation in the study:

- 1. Is a male or female \geq 60 years of age
- 2. Can understand the nature of the trial and protocol requirements and provide written informed consent.

If the subject is deemed not competent to provide informed consent, the following requirements for consent must be met:

- a. The subject's legally acceptable representative (LAR) (or study partner/caregiver, if local regulations allow) must provide written informed consent
- b. The subject must provide written (if capable) informed assent
- 3. Subject requires some or complete assistance with one or more of the following:
 - a. Instrumental activities of daily living (communication, transportation, meal preparation, shopping, housework, managing medications, managing personal finances) OR
 - b. Basic activities of daily living (personal hygiene, dressing, eating, maintaining continence or transferring)
- 4. Meets clinical criteria for at least one of the following disorders, with or without cerebrovascular disease (CVD):
 - a. Parkinson's disease with or without dementia as defined by the Movement Disorder Society's Task Force (Appendix B)
 - b. Dementia with Lewy bodies (DLB) (Appendix C)
 - c. All-cause dementia, possible or probable Alzheimer's disease (AD) (Appendix A)
 - d. Frontotemporal degeneration spectrum disorders, including possible or probable:
 - i. Behavioral variant frontotemporal dementia (Appendix D)
 - ii. Progressive supranuclear palsy (Appendix E)
 - iii. Corticobasal degeneration (Appendix F)

Study: ACP-103-046 Clinical Study Protocol Amendment 7 Date: 5 March 2021

> e. Vascular dementia, including post-stroke dementia, multi-infarct dementia and/or subcortical ischemic vascular dementia (SIVD) (Appendix G)

- 5. Has an MMSE score ≥6 at Visit 1 (Screening) and Visit 2 (Baseline)
- 6. Has neuropsychiatric symptoms severe enough to warrant treatment with an antipsychotic agent, as evidenced by the Neuropsychiatric Inventory (NPI) score (Frequency×Severity) ≥4 on at least one of the following domains at Visit 1 (Screening) and Visit 2 (Baseline) (the domains at Screening and Baseline can be different):
 - a. Domain A Delusions; OR
 - b. Domain B Hallucinations: OR
 - c. Domain D Depression/Dysphoria; OR
 - d. Domain G Apathy/Indifference; OR
 - e. Domain H Disinhibition; OR
 - f. Domain I Irritability/Lability; OR
 - g. Domain K Sleep

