14.1.1 Primary Safety Analyses

TEAEs are the primary measure for this study. For the following summaries, the event counts and the number and percentage of subjects reporting TEAEs will be tabulated by treatment group:

- TEAEs by SOC and preferred term (PT)
- Most frequently reported TEAEs by SOC and PT
 - PTs reported by \geq 5% of subjects in either treatment group
- TEAEs by PT
- TEAEs by maximum severity, SOC, and PT
 - if more than 1 AE occurs with the same PT for the same subject, the subject will be counted only once for that PT using the most severe occurrence
- TEAEs related to study drug by SOC and PT
- Treatment-emergent serious adverse events (TESAEs) by SOC and PT
- TEAEs leading to study drug discontinuation or study termination by SOC and PT
- AEs with fatal outcome by SOC and PT
- TEAEs with fatal outcome (that occurred within 30 days of last dose) by SOC and PT

For tabulations that include SOC and PT the display will be sorted alphabetically by SOC and then by descending subject frequency for the PTs based on counts in the combined treatment groups within each SOC. SOCs will not be included in the TEAEs by PT tabulation. This display will be sorted by descending subject frequency based on counts in the combined treatment groups.

An AE listing by subject will display all events, including those which are not treatmentemergent, and will include the verbatim term in addition to the MedDRA SOC and PT. This listing will also include all relevant eCRF data associated with the event: e.g. date of onset, date resolved, date of the first and last dose of study drug, severity, frequency, outcome, relationship to study drug, action taken with study drug, and required therapy. When a date is presented, the study day associated with the date will also be displayed. Separate listings will be presented for subjects with SAEs, subjects with AEs leading to study drug discontinuation or study termination and subjects who died (if any). In these listings, an indicator for TEAEs will also be included.

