14.1.2 Assessment of the Impact of COVID-19 on Adverse Events

The relationship of selected AEs to COVID-19 will be assessed by investigator as detailed in the DMP Appendix B, for those subjects who were not unblinded as part of the first interim analysis. Each of the primary safety analyses described in Section 14.1.1 will be additionally summarized by relationship to COVID-19 (Not related to COVID-19 vs. Related to COVID-19).

Both the Not related to COVID-19 and the Related to COVID-19 AE tables will be summarized using 2 sets of subjects: all subjects in the Safety analysis set, and subjects in the Safety analysis set that were not included in IA-1, as a proxy for pre- and post-COVID-19 analyses.

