19 CHANGES TO ANALYSES SPECIFIED IN PROTOCOL

Added DRP, AD, ADP, and Other subgroups, statistical tests for treatment comparisons of efficacy and secondary safety variables, and data handling related to Ukraine geopolitical conflict.

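### Does the SAP need adverse-event tables for its dementia and psychosis subgroups, and a tighter definition of Other-dementia psychosis?

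*SAP*

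**What the plan says.** SAP 12.5 sits in the efficacy chapter and opens: "Treatment comparisons will be made with respect to exploratory efficacy and secondary safety variables separately for each subgroup by" four groups, namely dementia-related psychosis (DRP), dementia with Alzheimer's disease (AD) as primary cause, AD psychosis (ADP) and Other-dementia psychosis. SAP 14.2 identifies the secondary safety endpoints as ESRS-A and MMSE.

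Adverse events are handled in SAP 14.1.1, which states that "TEAEs are the primary measure for this study". TEAE tables are by treatment group: overall, by severity, related, serious, leading to discontinuation, and fatal. Subject listings accompany them. Two repeats are planned. SAP 14.1.2 says "Each of the primary safety analyses described in Section 14.1.1 will be additionally summarized by relationship to COVID-19", for the whole Safety Analysis Set and for those outside the first interim analysis. SAP 3.7 reruns all analyses without the affected Ukraine subjects. Neither is a split by diagnosis. SAP 1 places table specifications in a separate document.

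On definitions, ADP is "Subjects with AD as the primary cause of dementia" with a Baseline NPI delusions or hallucinations score of at least 2. Other-dementia psychosis is "Subjects with vascular dementia, frontotemporal dementia-spectrum disorders, or dementia with Lewy bodies, and having either a Baseline NPI delusions or hallucinations score" at the same threshold, with no mention of primary cause. Protocol 4.2, criterion 4, admits a subject who "Meets clinical criteria for at least one of the following disorders".

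**The concern.** The trial has a primary safety objective. SAP 1 says the subgroups and formal comparisons were added to support possible regulatory submissions, and Protocol 1.3.1 cites a boxed warning that "elderly patients with dementia-related psychosis treated with antipsychotic drugs are at an increased risk of death". A reader of the results would find estimates and nominal p-values for efficacy in DRP and ADP, but no table beside them of serious or fatal TEAEs in the same subjects. That looks like benefit without risk in the population where risk matters most.

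The second worry is that a row labelled Other suggests subjects who are not in the AD rows, while its definition does not secure this. If some subjects count in both ADP and Other, a reader could take two partly shared results as independent of each other.

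**Working it through.** **Scope of the subgroup text.** SAP 12.5 limits treatment comparisons to exploratory efficacy, ESRS-A and MMSE. SAP 19 reads "Added DRP, AD, ADP, and Other subgroups, statistical tests for treatment comparisons of efficacy and secondary safety variables". In that list the limit to efficacy and secondary safety belongs to the tests, not to the subgroups. So the SAP plans no TEAE table by diagnosis, but nothing in it rules out a descriptive one.

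**What such a table could show.** The plan's own figure comes first. With 375 per arm (SAP 3.5), the chance of at least one event is 1 − (1 − p)^375:

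- p = 1.0%: 0.977
- p = 1.5%: 0.997
- p = 2.0%: 0.9995, stated as 0.999

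These agree with the SAP.

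The documents do not give the share of subjects in each subgroup. Assume 20% to 70% of each arm, so n = 375 × 0.2 = 75 to 375 × 0.7 = 262 (rounded down). For the last row, assume a TEAE category with 10% incidence in both arms.

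| Quantity | Formula | n = 75 | n = 262 | n = 375 |
|---|---|---|---|---|
| Chance of at least one event at 1% | 1 − 0.99^n | 0.529 | 0.928 | 0.977 |
| One-sided 95% upper limit if no events are seen | 1 − 0.05^(1/n) | 3.9% | 1.1% | 0.8% |
| 95% CI half-width for a difference, 10% in each arm | 1.96 × √(2 × 0.1 × 0.9 / n) | 9.6 points | 5.1 points | 4.3 points |

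A subgroup TEAE table would therefore describe what occurred. It could seldom establish or exclude a moderate difference between arms.

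**What is lost by not planning it.** SAP 14.1 already fixes the TEAE definition and categories. SAP 12.5 already defines the subgroups from the cause of dementia and the Baseline NPI, both recorded before treatment. A later table applies an existing subgroup flag to an existing display. It needs no new data and spends no alpha, and it leaves the analyst little room for choice.

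**The overlap.** Take three yes/no features: AD as primary cause; vascular, frontotemporal-spectrum or Lewy body dementia present; NPI score of at least 2. Of the 2 × 2 × 2 = 8 combinations, exactly one meets both ADP and Other as literally defined, the one with all three present. Protocol 4.2 allows it. The documents do not say how many subjects have it.

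**What the overlap does.** SAP 12.5 analyses each subgroup separately. It plans no contrast between subgroups and no pooling across them, and SAP 12.4 makes no multiplicity adjustment. The rows are not a partition in any case, since ADP lies inside both AD and DRP by definition. A subject in two rows is therefore counted once in each of two separate models, and each still compares randomised arms.

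**The case for a change.** The strongest reply is that imprecision applies equally to benefit. If DRP and ADP are large enough for efficacy estimates with p-values, they are large enough for a count of serious and fatal TEAEs, and a safety trial should commit to showing its primary measure wherever it shows efficacy. This has force as advice on presentation, and four repeat tables would be cheap. It does not show a planned result to be wrong. The primary objective concerns the whole enrolled population, in which TEAEs are tabulated in full and reviewed by the DSMB (SAP 17). Section 12.5 also already carries two safety endpoints into the subgroups.

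The link to the warning is looser than it first appears. DRP in SAP 12.5 is dementia from any cause with psychosis, so it can include Parkinson's disease dementia, whereas the statement in Protocol 1.3.1 on where the drug is not approved sets Parkinson's disease psychosis apart.

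On the overlap, it is fair to say that the wording is incomplete. However, a programmer needs a primary-cause item to build the AD and ADP rows, and the same item settles Other in the way its label suggests.

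**Conclusion.** No change follows. The SAP text plans no TEAE summary by diagnosis subgroup, and the definition of Other-dementia psychosis is looser than those of AD and ADP. The first is a choice of display. Under the assumed shares of 20% to 70% the added tables would be descriptive only, with a 0.53 to 0.93 chance per arm of seeing an event of 1% incidence, and they can be produced on request. The second is a wording gap that analysts can fill sensibly. It biases no estimate, and its size is unknown.

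This rests on two assumptions. The eCRF is taken to record a primary cause of dementia: Protocol 6.1.5 says only that details of the diagnosis are collected, but the AD and ADP rows already depend on such an item. The subgroup results are taken to be read one row at a time, as SAP 12.5 plans them. A planned contrast of ADP against Other would make the overlap matter, and the SAP has none.
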